### 2.2. Study Period:

This sub-study is planned over an 18-month period, from July 2025 to January 2027, running alongside the NP Resistome study (Protocol v5.0 COMREC reference P.10/24-1200). Activities include sample aliquoting, international shipment, laboratory testing using the ssUAD assay, data integration, statistical analysis, and dissemination of findings.

MALAWI LIVERPOOL  
WELLCOME PROGRAMME

[figure not shown]

KAMUZU  
UNIVERSITY  
OF HEALTH SCIENCES

These activities will be carried out in sequential and overlapping phases, aligned with the timelines and logistics of the parent study. Community and hospital-based participant samples collected through NP Resitome will be utilised throughout.

A detailed timeline of the sub-study activities is presented in the Gantt chart below, outlining the expected duration and sequencing of each phase.

	July - August 2025	September- October 2025	November- December 2025	January- February 2026	March – April 2026	June- July 2026	August – September 2026	October- November 2026	December 2026 – January 2027
Urine sample aliquoting and storage									
Shipping of urine samples to the UK									
ssUAD testing at Nottingham/UK HSA									
Compile carriage and metagenomic data									
Data cleaning and linkage									
Data analysis (prevalence, regression, ROC)									
Write-up and report preparation									

MALAWI LIVERPOOL  
WELLCOME PROGRAMME

KAMUZU  
UNIVERSITY  
OF HEALTH SCIENCES

Dissemination  
(thesis, papers,  
conferences)

**Figure 1. Study timeline**

All urine samples collected as part of this sub-study will be stored at the Malawi-Liverpool-Wellcome (MLW) Programme for up to five years following study completion, in accordance with institutional and ethical guidelines. Upon conclusion, final reports will be submitted to COMREC, the Blantyre District Health Office, and the study sponsor (LSTM), alongside dissemination to scientific and policy stakeholders.

### **2.3. Inclusion and Exclusion criteria:**

This sub-study will use existing urine samples that have already been collected as part of the NP Resistome study (COMREC reference P.10/24-1200). The inclusion criteria applied during that study were: children aged 12–24 months residing in Blantyre District whose parents or legal guardians provided written informed consent.

[figure not shown]
As no new participant recruitment or sample collection will be undertaken, no additional inclusion or exclusion criteria are applicable for this sub-study.

### **2.4. Sample collection and handling:**

This sub-study will use existing urine specimens that have already been collected as part of NP Resistome study. Up to 5 ml of urine was collected per participant using sterile paediatric urine collection bags. Each specimen was aliquoted into three 1.5 ml cryovials and stored at –80 °C until analysis. All specimens were Pseudonymised and linked to participants only through study ID numbers, in accordance with data protection protocols.

### **2.5. Laboratory analysis:**

Urine samples will be analysed using the ssUAD, a Luminex-based immunoassay designed to detect pneumococcal polysaccharide capsules. Testing will follow validated protocols and will be conducted at an accredited reference laboratory with expertise in multiplex immunoassay

MALAWI LIVERPOOL  
WELLCOME PROGRAMME

KAMUZU  
UNIVERSITY  
OF HEALTH SCIENCES

techniques at the University of Nottingham NHS Trust, UKHSA and PATH based in Seattle, USA.

### **2.6. Sample size:**

The minimum required sample size for this study is 147 urine specimens, accounting for a 10% allowance for non-response or data loss. This estimate is based on detecting a significant difference in pneumococcal serotype-specific antigen detection between children hospitalised with pneumonia, those treated at health centres, and healthy community controls.

[figure not shown]
The core sample size calculation indicates that at least 49 specimens per group are needed, assuming antigen detection rates of 70% in hospitalised children, 53% in health centre cases, and 35% in healthy controls, based on prior studies. Using a two-sided significance level of 0.05 and 80% statistical power, the estimated minimum total sample size is 147 participants across the three groups.

To address the limitation of a small sample size faced in our preliminary analysis of 214 urine specimens from hospitalised children, we plan to test all 350 urine specimens collected under the parent NP Resistome study. This expanded approach will improve the precision of our estimates, allow for subgroup analyses, and provide broader insights into pneumococcal antigen detection patterns across the study groups

### **2.7. Data management:**

All data generated from this sub-study will be managed in alignment with the main NP Resistome study (COMREC reference P.10/24-1200). Urine specimens will be labelled using the same barcoded identifiers already assigned under the NP Resistome framework. No new study identifiers will be created.

Data will be entered into a secure, password-protected electronic database with access restricted to authorised study personnel. To ensure data accuracy and completeness, double data entry procedures and regular validation checks will be implemented.

MALAWI LIVERPOOL  
WELLCOME PROGRAMME

KAMUZU  
UNIVERSITY  
OF HEALTH SCIENCES

All data will be used solely for the objectives described in this protocol and handled in accordance with institutional data governance policies and COMREC ethical approvals. No personally identifiable information will be included in shared datasets or reported results.

## **2.8. Data analysis:**

The data analysis plan is structured to address the study's three specific objectives:

### **2.8.1. Prevalence and distribution (objective 1):**

Descriptive statistics (frequencies, means, medians) will be used to summarise participant characteristics across study groups. Serotype-specific prevalence of urinary pneumococcal antigens will be calculated for each group, hospitalised pneumonia, community-managed pneumonia, and healthy controls. Differences between groups will be assessed using chi-square tests or Fisher's exact test, as appropriate.

[figure not shown]

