Serotype-specific urinary antigen detection (ssUAD) has emerged as a promising non-invasive tool for diagnosing and serotyping pneumococcal pneumonia. The ssUAD test is a 25-plex Luminex-based extended-range urine antigen capture assay developed by UKHSA, which has shown favourable results for diagnosing pneumococcal disease among adult patients in the UK. The 24-serotype-specific urine antigen detection (24ssUAD) assay can detect pneumococcal capsular polysaccharide antigens in urine, offering greater diagnostic sensitivity than the culture-based method. The current version of ssUAD targets 24 pneumococcal serotypes and has a sensitivity of 96.2% and specificity of 89.9% among adults with community-acquired pneumonia or invasive pneumococcal disease in the UK. However, there is limited data on the surveillance and diagnostic performance of ssUAD in high-carriage and disease-burden settings, such as Malawi, where asymptomatic or healthy children may also shed pneumococcal antigens in urine, making it more challenging to distinguish invasive disease. Unpublished data from our testing of the 24ssUAD assay on historical urine samples from Malawian children

MALAWI LIVERPOOL  
WELLCOME PROGRAMME

KAMUZU  
UNIVERSITY  
OF HEALTH SCIENCES

[figure not shown]
with acute respiratory infection (ARI) indicate that pneumococcal antigens can be detected in urine, suggesting the assay's potential utility in such settings and highlighting the need for further evaluation to distinguish between carriage and disease. The data also revealed that pre-hospital antibiotic exposure significantly reduced the sensitivity of culture-based methods, decreasing pneumococcal detection rates from 81% to 21%, highlighting the potential diagnostic advantage of urine antigen assays in such contexts.

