#### **1.4.2. Specific objectives**

1. Determine the prevalence of serotype-specific pneumococcal antigens in urine among children under five years of age with pneumonia compared to healthy counterparts.

MALAWI LIVERPOOL  
WELLCOME PROGRAMME

KAMUZU  
UNIVERSITY  
OF HEALTH SCIENCES

2. To characterise the association between the detection of serotype-specific antigens in urine and nasopharyngeal pneumococcal carriage among children.
3. To define revised ssUAD thresholds that distinguish pneumococcal carriage from disease, to support field evaluations and inform diagnostic and surveillance strategies in Malawi and similar settings.

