### **2.8.3. Defining diagnostic thresholds (objective 3):**

Signal intensity data (median fluorescence intensity or equivalent) from the 24ssUAD assay will be analysed to compare antigen profiles between cases (pneumonia) and carriers (healthy children). Receiver Operating Characteristic (ROC) curve analysis will be used to define optimal cut-off values for distinguishing pneumococcal disease from carriage. Area under the curve (AUC) values will quantify diagnostic performance. Findings will be cross-referenced with previously published UK datasets to support broader applicability.

All analyses will be conducted using R software, with statistical significance defined at  $p < 0.05$  and confidence intervals at 95%. Graphical data presentation will include bar charts, ROC curves, and stratified prevalence plots.

MALAWI LIVERPOOL  
WELLCOME PROGRAMME

KAMUZU  
UNIVERSITY  
OF HEALTH SCIENCES

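### Objective 1, on its natural reading, tests 24 serotype prevalences across three groups at p < 0.05 each with no control across serotypes, while the sample size rests on one detection rate per group

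*Protocol*

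**What the plan says.** The first specific objective (Protocol 1.4.2) is serotype-specific: "Determine the prevalence of serotype-specific pneumococcal antigens in urine among children under five years of age with pneumonia compared to healthy counterparts". Section 1.0 gives the number of serotypes: "The current version of ssUAD targets 24 pneumococcal serotypes".

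Section 2.8.1 turns the objective into an analysis: "Serotype-specific prevalence of urinary pneumococcal antigens will be calculated for each group, hospitalised pneumonia, community-managed pneumonia, and healthy controls". The next sentence reads "Differences between groups will be assessed using chi-square tests or Fisher's exact test, as appropriate". No other antigen measure is named there as the thing compared.

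The decision rule stands at the end of section 2.8.3 and covers every objective: "All analyses will be conducted using R software, with statistical significance defined at" p < 0.05, with 95% confidence intervals.

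Section 2.6 justifies the sample size on one rate per group, "assuming antigen detection rates of 70% in hospitalised children, 53% in health centre cases, and 35% in healthy controls". It plans to test all 350 specimens of the parent study. The protocol names no primary serotype, no overall test that must succeed first, no adjustment, and no exploratory label for the serotype comparisons.

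**The concern.** A 5% threshold limits false positives for one test. Applied separately to 24 serotypes, it leaves the chance of a false difference somewhere in the family far above 5%. The executive summary says the findings will inform surveillance, pneumonia diagnostics and vaccine impact assessment. A serotype that crosses p < 0.05 by chance could then be reported as more common in pneumonia than in healthy children, in a study whose purpose is to separate disease from carriage.

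There is also a mismatch. The comparison behind the sample size has one outcome per child, whereas the comparison written into 2.8.1 has 24.

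**Working it through.** **Inputs from the protocol.** 24 serotypes (1.0); three groups and chi-square or Fisher's exact tests (2.8.1); p < 0.05 for all analyses (2.8.3); 350 specimens; detection rates of 70%, 53% and 35% (2.6).

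**Assumptions, because the protocol does not give them.** Groups of 117, 117 and 116; one three-group test per serotype; serotypes independent unless stated otherwise; the prevalence of each serotype as set out below.

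**The plan's own figure.** The protocol states no family-wise error rate. Its only related figure is 49 per group, 147 in total, at "Using a two-sided significance level of 0.05 and 80% statistical power". For a three-group chi-square test (2 df, noncentrality 9.63):
- the mean rate is (0.70 + 0.53 + 0.35)/3 = 0.527;
- the squared deviations sum to 0.0613;
- n = 9.63 × (0.527 × 0.473)/0.0613 ≈ 39.2, so 40 per group;
- with 10% loss, 40/0.9 gives 45 per group, or 135.

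This does not reproduce 49. That is a separate matter and does not affect this point. What matters here is that the calculation uses one rate per group.

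**Nominal error across 24 tests, no serotype differing.**
- Chance of at least one false positive: 1 − 0.95^24 = 0.708.
- For comparison, Bonferroni at 0.05/24 = 0.00208 gives 1 − (1 − 0.00208)^24 = 0.049.

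**Allowing for discreteness.** With few positives per serotype, the tests reject less often than 5%. If s_j is the exact rejection rate for serotype j, the family-wise error is 1 − Π(1 − s_j).

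With one common prevalence for all serotypes:

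| Prevalence | Size, Fisher / chi-square | Error over 24, Fisher / chi-square |
|---|---|---|
| 1.5% | 0.029 / 0.040 | 0.51 / 0.63 |
| 3% | 0.044 / 0.045 | 0.66 / 0.67 |
| 5% | 0.047 / 0.047 | 0.69 / 0.69 |
| 10% | 0.049 / 0.049 | 0.70 / 0.70 |

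The last row lies outside the protocol's own rates: 10% for each of 24 independent serotypes implies 1 − 0.9^24 = 92% of children positive for some antigen.

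Tying the prevalences to the protocol's rates for any antigen, either equal across serotypes or skewed (each 0.85 times the one before), gives:

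| Any antigen | Equal, Fisher | Skewed, Fisher | Skewed, chi-square |
|---|---|---|---|
| 35% | 0.55 | 0.43 | 0.52 |
| 53% | 0.67 | 0.52 | 0.59 |
| 70% | 0.69 | 0.57 | 0.63 |

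**Sensitivity.**
- A latent correlation of 0.2 between serotypes moves the Fisher results by about 0.03 at most.
- A split of 150/100/100 gives 0.45 to 0.59 for skewed Fisher. A split of 100/50/200 gives 0.49 to 0.61, and skewed chi-square then reaches 0.73.
- With only 49 per group, Fisher with equal prevalences gives 0.17 to 0.53 over the same any-antigen rates. The protocol plans 350 specimens, not 147.

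**The case against.** The strongest reply is that multiplicity is usually settled in a statistical analysis plan, which may exist, and that p < 0.05 could be applied to adjusted p-values. This stands in part: a later plan could repair the matter. But the protocol is not silent. It fixes one threshold for all analyses directly after describing serotype-specific comparisons, and on its face that is 5% per test.

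Second, 2.8.1 does not spell out one test per serotype, and objective 1 is largely estimation. This also stands, so the point is put as the natural reading. It remains the natural one because serotype-specific prevalence is the only antigen measure named before the tests.

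Third, the thresholds separating disease from carriage come from the ROC analysis of signal intensity, so no formal decision hangs on one serotype's p-value. That is correct, and it limits the harm to how serotype findings are reported and read.

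Fourth, a reader might infer from 0.71 that a false serotype difference is more likely than not, or that one is to be expected. The documents do not support either. The error falls to 0.43 under a skewed distribution with 35% antigen-positive, and the expected number of false positives is below one in sparse cases (24 × 0.029 = 0.70 at 1.5% prevalence). A reader might also multiply the count by three for pairwise contrasts, but the protocol names none.

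Finally, no serotype differing is a benchmark, since the protocol expects overall detection to differ. True differences in some serotypes do not protect the rest: with 12 true nulls the nominal error is still 1 − 0.95^12 = 0.46.

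**Conclusion.** The point holds as a cheap improvement to the analysis. On their natural reading, sections 2.8.1 and 2.8.3 judge 24 serotype comparisons at 5% each without control across them, while section 2.6 supports one comparison. The family-wise error is 0.71 nominally and about 0.43 to 0.70 once discreteness is allowed for. It stays within 0.43 to 0.69 when the any-antigen rate is held to the protocol's 35% to 70%. These figures rest on 350 specimens, the assumed near-equal group sizes, the assumed serotype distributions, one three-group test per serotype, and no true differences. The exact value is uncertain and can lie on either side of one half; that it is far above 5% is not in doubt under these assumptions. The data collected are unaffected; only the rule for declaring a serotype difference needs to change.

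**What to change.** In section 2.8.1, name one child-level comparison, any serotype antigen detected versus none across the three groups, and apply p < 0.05 to it. This matches the single rate per group in section 2.6.

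State that individual serotype differences will be declared only after Benjamini-Hochberg at 5% across the 24 serotypes, or after a permutation min-p (Westfall-Young) procedure that permutes group labels. The two control different things. Benjamini-Hochberg limits the expected share of false findings among the serotypes flagged. The permutation procedure limits the chance of any false finding and uses the discreteness and correlation in the data. Choose one before the results are seen.

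Report a 95% interval for each prevalence difference; section 2.8.3 already adopts 95% intervals but does not say they apply to differences. Amend the general p < 0.05 sentence in 2.8.3 to refer to this rule.

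The cost is a few sentences and standard R functions, with no change to specimens, assays or budget. The downside is somewhat lower power to flag a single serotype, which the permutation procedure limits.

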### **2.8.2. Association with carriage dynamics (objective 2):**

Logistic regression models will be employed to assess the association between urinary antigen detection (the outcome variable) and nasopharyngeal carriage (the predictor), adjusting for potential confounders such as age, antibiotic use, and HIV status. Subgroup analyses will examine the influence of carriage density and serotype co-carriage on antigen detection. Multivariable regression and interaction terms will help explore effect modification.

### **2.8.3. Defining diagnostic thresholds (objective 3):**

Signal intensity data (median fluorescence intensity or equivalent) from the 24ssUAD assay will be analysed to compare antigen profiles between cases (pneumonia) and carriers (healthy children). Receiver Operating Characteristic (ROC) curve analysis will be used to define optimal cut-off values for distinguishing pneumococcal disease from carriage. Area under the curve (AUC) values will quantify diagnostic performance. Findings will be cross-referenced with previously published UK datasets to support broader applicability.

All analyses will be conducted using R software, with statistical significance defined at  $p < 0.05$  and confidence intervals at 95%. Graphical data presentation will include bar charts, ROC curves, and stratified prevalence plots.

MALAWI LIVERPOOL  
WELLCOME PROGRAMME

KAMUZU  
UNIVERSITY  
OF HEALTH SCIENCES

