## 2.0 Methodology

### 2.1. Study Design and Setting:

This case-control sub-study is nested within the NP Resistome study (Protocol v5.0 COMREC reference P.10/24-1200), a prospective observational cohort conducted in Blantyre, Malawi. Recruitment will take place at Ndirande Health Centre (NHC), Gateway Primary Care Centre (GPCC), and Queen Elizabeth Central Hospital (QECH). The sub-study will involve the analysis of urine samples that have already been collected from children aged 12–24 months across four defined participant groups in the parent NP Resistome study.

[figure not shown]
Study Population:

Participants will be children aged 12–24 months enrolled in the NP Resistome study (COMREC reference P.10/24-1200) in the following groups;

- Children hospitalised with pneumonia at QECH.
- Children with pneumonia treated at primary health centres (i.e NHC).
- Healthy community controls with and without recent antibiotic exposure.

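### Objective 3 takes its cut-off and AUC from all pneumonia cases together, so both depend on an undefined mix of hospitalised and health-centre children

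*Protocol*

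**What the plan says.** Protocol Section 2.8.3 sets one two-class comparison of signal intensity: "compare antigen profiles between cases (pneumonia) and carriers (healthy children". It continues: "Receiver Operating Characteristic (ROC) curve analysis will be used to define optimal cut-off values for distinguishing pneumococcal disease from carriage". AUC is the measure of performance. The section mentions no split of cases by care setting and no split or adjustment by antibiotic exposure.

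The Study Population list in Section 2.1 shows what each class contains. The pneumonia groups are "Children hospitalised with pneumonia at QECH" and "Children with pneumonia treated at primary health centres (i.e NHC"). The control group is "Healthy community controls with and without recent antibiotic exposure".

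Section 2.6 plans on different detection in the two pneumonia groups: "assuming antigen detection rates of 70% in hospitalised children, 53% in health centre cases, and 35% in healthy controls".

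The other two objectives handle these factors explicitly. Section 2.8.1 calculates prevalence in three separate groups, and Section 2.8.2 adjusts for antibiotic use. Section 2.6 says that testing all 350 specimens will permit subgroup analyses, but does not link these to the ROC work. The stratified plots named in Section 2.8.3 are of prevalence. The document gives no breakdown of the 350 specimens by group.

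**The concern.** An ROC curve for a case class made of two groups is a weighted average of the two groups' curves, and the weights are the numbers recruited. If the groups differ, as the protocol expects, the pooled AUC and sensitivity lie between the two groups' values, and the chosen cut-off moves with the weights.

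The threshold is the main product of objective 3. It is meant to support later field evaluations and to inform diagnostic and surveillance strategies in Malawi and similar settings (Section 1.4.2). On the planning rates, a pooled sensitivity or AUC would overstate performance in community-managed pneumonia and understate it in hospitalised pneumonia. A later study with another case mix could find a different AUC and cut-off with no change in the assay.

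**Working it through.** **The plan's own figure.** The protocol states no AUC, cut-off, sensitivity or specificity for objective 3, so there is none to reproduce. Its only related figure is 49 per group (147 in total) in Section 2.6. The inputs there are "Using a two-sided significance level of 0.05 and 80% statistical power" and, for the total, "accounting for a 10% allowance for non-response or data loss". On those inputs a three-group chi-square test needs 40 per group, or 45 after 10% loss, so 49 is not reproduced. That is a separate matter and has no bearing on this point.

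**Inputs.** Detection rates of 0.70 (hospitalised), 0.53 (health centre) and 0.35 (healthy), from Section 2.6. The last gives a specificity of 1 − 0.35 = 0.65 at the planning threshold. The hospitalised share of cases, w, is not in the protocol, so a range is shown.

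**Step 1: sensitivity at the planning threshold.** Pooled sensitivity = 0.70w + 0.53(1 − w).

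- w = 0.20: 0.140 + 0.424 = 0.564
- w = 0.50: 0.350 + 0.265 = 0.615
- w = 0.80: 0.560 + 0.106 = 0.666

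This needs no distributional assumption.

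**Step 2: AUC.** Against the same controls, pooled AUC = w × AUC(hospitalised) + (1 − w) × AUC(health centre), whatever the distributions. Values for the two AUCs need a model. Assume normal signals with equal variance, anchored at the three planning rates:

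- Hospitalised shift from the healthy mean: z(0.70) + z(0.65) = 0.524 + 0.385 = 0.910 SD. AUC = Φ(0.910/√2) = 0.740.
- Health-centre shift: z(0.53) + z(0.65) = 0.075 + 0.385 = 0.461 SD. AUC = Φ(0.461/√2) = 0.628.
- Pooled at w = 0.20: 0.148 + 0.502 = 0.650. At w = 0.80: 0.592 + 0.126 = 0.718.

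**Step 3: cut-off.** Section 2.8.3 does not say how the optimum is chosen; the Youden index is assumed here. Under the same model:

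| Hospitalised share of cases | AUC | Cut-off (SD above healthy mean) |
|---|---|---|
| 0% | 0.628 | 0.230 |
| 25% | 0.656 | 0.315 |
| 50% | 0.684 | 0.376 |
| 75% | 0.712 | 0.421 |
| 100% | 0.740 | 0.455 |

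At the 50% cut-off of 0.376, pooled sensitivity is 0.619. The two groups have Φ(0.910 − 0.376) = 0.70 and Φ(0.461 − 0.376) = 0.53, so the pooled value describes neither.

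**Step 4: controls.** The document gives no detection rate by antibiotic exposure in healthy children, so only an illustration is possible. Let the exposed share of controls run from 25% to 75%. If the two strata had rates of 30% and 40%, pooled specificity would range over 62.5% to 67.5%. With 25% and 45% it would range over 60% to 70%. With equal rates it stays at 65%. Which stratum would be higher is also unknown.

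**Step 5: precision of separate analyses.** Take 49 cases, 49 controls and AUC = 0.63, with the Hanley-McNeil variance. Q1 = 0.63/1.37 = 0.460, Q2 = 2(0.63²)/1.63 = 0.487 and 0.63² = 0.397. Variance = [0.63 × 0.37 + 48(0.460 − 0.397) + 48(0.487 − 0.397)]/49² ≈ 0.0032, so SE ≈ 0.056. The 95% interval is 0.63 ± 0.11, or about 0.52 to 0.74.

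**The case against.** The strongest reply is that Section 2.8.3 names the classes but never says that groups will be pooled or that only one curve will be fitted. Stratified ROC detail is often left to an analysis plan, and Section 2.6 foresees subgroup analyses. It is right that pooling is the plain reading and is not written out. But the section does fix the two classes from which cut-offs and AUC come. Unlike Sections 2.8.1 and 2.8.2, it carries no group split or adjustment, and the subgroup analyses are not tied to the threshold.

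A second reply is that the figures do not measure objective 3 itself. The planning rates belong to an existing positivity rule and are not serotype-specific, the binormal model is not the protocol's, and 53% lies close to the midpoint of 70% and 35% (52.5%), so it may be an interpolation. This limits the exact values. It does not remove the dependence on mix, which holds whenever the groups differ, and the protocol plans on a 17-point difference.

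Third, separate estimates will be imprecise. This stands: at 49 per group, the interval for an AUC of 0.63 reaches 0.74, the value modelled for hospitalised cases.

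A reader might also infer several stronger points that the documents do not support:

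- That the result is driven by recruitment quotas. No quotas or group sizes are given, only a recruited mix.
- That the pooled figures describe no real population. They describe one with the same mix; the fault is that the mix is undefined.
- That the threshold is intended for primary care. Health centres appear as a recruitment setting, and the stated purpose is field evaluation and strategy.
- That mixing antibiotic-exposed and unexposed controls biases specificity. No rates by exposure are given, the effect is zero if they are equal, and Section 1.1 says that urinary antigen tests keep their sensitivity after antibiotics.

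**Conclusion.** The point holds on the case side. Followed as written, Section 2.8.3 gives an AUC, a cut-off and an implied sensitivity that vary with a case mix the protocol neither defines nor justifies. On the protocol's own rates, pooled sensitivity varies by about 10 percentage points (56% to 67%, unrounded 56.4% to 66.6%) as the hospitalised share of cases goes from 20% to 80%. That figure needs only the planning rates. The AUC range of 0.65 to 0.72 and the movement of the cut-off also rest on the equal-variance binormal model and, for the cut-off, on the Youden index. On the control side, the recruited mix of antibiotic exposure is a reason to report specificity by stratum, not evidence of bias.

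**What to change.** In Section 2.8.3, state that AUC, cut-off and sensitivity, each with a 95% confidence interval, will be reported separately for hospitalised and for community-managed pneumonia against healthy children. Give any pooled result only with the number of cases from each group beside it. Base conclusions for each setting on the matching group. As a secondary check, report specificity at the chosen cut-off in controls with and without recent antibiotic exposure.

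This needs a few sentences and extra ROC runs on specimens already due for testing, with no new recruitment or assay work. The real cost is precision. Intervals will be clearly wider, as the example of 0.52 to 0.74 at 49 per group shows, and group-specific cut-offs may be less stable than a pooled one. The protocol should acknowledge this, and should give the expected split of the 350 specimens by group so that the achievable precision can be judged.

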Available evidence primarily comes from adult populations where nasopharyngeal colonisation is relatively uncommon and less likely to interfere with urine-based antigen detection. In contrast, children in sSA, including Malawi, often exhibit high nasopharyngeal carriage rates, which may make it difficult to distinguish between antigenuria due to invasive disease and antigen spillover from asymptomatic carriage.

[figure not shown]
Limited data exist on the specificity of ssUAD in high-carriage paediatric populations, particularly in low-resource settings where distinguishing between pneumococcal disease and antigenuria from asymptomatic carriage remains challenging. As such, there is an urgent need for context-specific data to define serotype-specific thresholds that can accurately differentiate carriage from disease. Addressing this gap is critical for the optimal use of ssUAD in clinical diagnostics, disease surveillance, and vaccine impact evaluations in high-burden LMIC settings.

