### **1.3. Hypothesis**

We hypothesise that the ssUAD assay will show high sensitivity for detecting pneumococcal serotype-specific antigens in children with pneumonia, but background antigenuria due to asymptomatic carriage will necessitate revised thresholds for accurate disease attribution in this high-burden setting.

[figure not shown]

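### Section 2.8.3 does not name the unit of its ROC analysis; run per serotype, it could not place stable cut-offs for most of the 24 serotypes

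*Protocol*

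**What the plan says.** Section 2.8.3 of the protocol uses continuous signal intensity, takes all children with pneumonia as cases and healthy children as carriers, and says that "Receiver Operating Characteristic (ROC) curve analysis will be used to define optimal cut-off values for distinguishing pneumococcal disease from carriage". AUC values are to quantify performance. The unit of the ROC is not named.

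Other places bear on that unit:
- Section 1.0: "The current version of ssUAD targets 24 pneumococcal serotypes".
- Section 1.1 describes the gap as a need for data to "define serotype-specific thresholds that can accurately differentiate carriage from disease".
- Section 2.8.1: "Serotype-specific prevalence of urinary pneumococcal antigens will be calculated for each group".
- Section 1.4.2, objective 3: "To define revised ssUAD thresholds that distinguish pneumococcal carriage from disease, to support field evaluations and inform diagnostic and surveillance strategies", with no mention of serotype.

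Section 2.6 gives the only detection rates, "assuming antigen detection rates of 70% in hospitalised children, 53% in health centre cases, and 35% in healthy controls", and plans to test all 350 specimens. It sizes the comparison of detection between three groups. It does not size objective 3, and it does not divide the 350 by group.

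**The concern.** A per-serotype ROC labels every pneumonia case as diseased for every serotype. A child whose antigenuria is due to one serotype then counts as a case in the 23 curves for the others, where the child's signal is background. The optimal point on such a curve is driven mainly by how the background of cases and controls happens to fall, with little contribution from the few children who excrete that antigen.

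This touches the purpose of the sub-study. Section 1.3 hypothesises that "background antigenuria due to asymptomatic carriage will necessitate revised thresholds for accurate disease attribution", and objective 3 hands the thresholds on to field evaluation and surveillance. Cut-offs that would move substantially in a second sample, reported with the accuracy seen in the data that chose them, would be a weak product to hand on.

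**Working it through.** **No plan figure to reproduce.** The protocol gives no sample size or precision for objective 3. The stated 49 per group (3 x 49 = 147) belongs to the three-group comparison of detection rates and is not used below.

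**Inputs from the protocol.** 350 specimens; 24 serotypes; detection in 70%, 53% and 35% of hospitalised, health-centre and healthy children.

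**Assumptions, because the protocol is silent.** The rates refer to detection of any serotype. The three groups are equal, giving 233 cases and 117 controls. Serotypes are evenly spread, with either one serotype per positive child or independent serotypes.

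**1. Positives per average serotype.** Mean case rate = (0.70 + 0.53)/2 = 0.615.
- One serotype per child: cases 0.615/24 = 0.0256; controls 0.35/24 = 0.0146. Counts: 233 x 0.0256 = 6.0 and 117 x 0.0146 = 1.7.
- Independent serotypes: cases 1 - 0.385^(1/24) = 0.0390; controls 1 - 0.65^(1/24) = 0.0178. Counts: 233 x 0.0390 = 9.1 and 117 x 0.0178 = 2.1. This implies 24 x 0.0390/0.615 = 1.5 serotypes per positive case.
- Over splits from 175:175 to 262:88, the counts are 4.5-10.2 cases and 1.3-3.1 controls.

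So 1 - 0.0390 = 96.1% to 1 - 0.0256 = 97.4% of cases lack the antigen in question.

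**2. AUC for an average serotype, equal background.** AUC = (1 + p_case - p_control)/2 = (1 + 0.0256 - 0.0146)/2 = 0.5055, up to (1 + 0.0390 - 0.0178)/2 = 0.5106. Null SE = sqrt((n + m + 1)/(12nm)) = sqrt(351/(12 x 233 x 117)) = 0.033. The expected departure from 0.5 is at most about a third of one standard error. If background is higher in cases, by an assumed 0.3 SD, the AUC rises to about 0.59, but the cut-off then mainly separates background.

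**3. Where the optimal point falls.** Suppose the optimum is the maximum Youden index, which is an assumption. With continuous signal and no true difference, its expected in-sample value is about sqrt(pi/8)/sqrt(nm/(n + m)) = 0.627/sqrt(233 x 117/350) = 0.627/8.83 = 0.071. With equal background, the true index of an average serotype cannot exceed its case rate, 0.026-0.039. The chance peak is therefore larger than the signal. Simulation agrees: in-sample optimism in the index is about 0.07 per serotype and 0.04 for a pooled curve.

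**4. What remains estimable.** Specificity is tolerable: 115 of 117 controls below a cut-off has a 95% interval of 94-99.8%. Sensitivity among antigen-bearing cases is not: 5 of 6 gives 36-99.6%, and 8 of 9 gives 52-99.7%.

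**5. Uneven serotypes.** With an assumed 1/rank mix, the commonest serotype has a 26.5% share: 0.615 x 0.265 x 233 = 38 positive cases and 0.35 x 0.265 x 117 = 11 positive controls. Its AUC is (1 + 0.163 - 0.093)/2 = 0.535, or up to 0.549 under other signal shapes; that is 1.1-1.5 null standard errors. A common serotype may be workable; the rare ones are worse than the average.

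**6. Child-level contrast.** Any-serotype detection gives 233 x 0.615 = 143 positive cases and 117 x 0.35 = 41 positive controls. The AUC of detection is (1 + 0.615 - 0.35)/2 = 0.63, about four null standard errors from 0.5. The sample can support this analysis.

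**7. Combining cut-offs.** If any serotype above its cut-off made a child positive, and serotypes were independent, 90% panel specificity would need 0.9^(1/24) = 99.56% for each. That is 117 x 0.0044 = 0.5 of a control above each cut-off, so it cannot be read off serotype by serotype.

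**The case against.** The strongest reply is that section 2.8.3 does not commit to a per-serotype ROC. The phrase about serotype-specific thresholds comes from a literature review, objective 3 speaks only of revised thresholds, and a statistical analysis plan not at hand may name the unit. A pooled curve largely avoids the problem. This stands, and the point is conditional for that reason. But 2.8.3 does fix the contrast, the scale and the ROC-optimal rule, and it is their combination with the per-serotype reading that fails.

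A second reply is that 6-9 and 2 are not the sample size of the ROC. That also stands. A reader might infer that each curve rests on fewer than a dozen children; the protocol nowhere restricts the ROC to positives, and all 350 signals would enter. What is poorly determined is the placement of the cut-off and its sensitivity.

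Third, a reader might infer that the resulting panel would flag most healthy children. The documents do not support this. Simulated panel false-positive rates ran from 4% to 100% depending on the background model, and they needed a Youden rule and an any-serotype rule that the protocol does not state.

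Fourth, AUC values and 95% intervals are to be reported, so an uninformative serotype would be visible, and field evaluation is meant to follow. This softens the consequence. It does not correct accuracy estimated in the same data that chose the cut-off.

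**Conclusion.** The concern holds conditionally. If the ROC is run per serotype, an average serotype offers about 6-9 positive cases and about 2 positive controls, an AUC near 0.51 with a null standard error of 0.033, and an optimal point dominated by chance. A dominant serotype, with perhaps 38 and 11, may be an exception. If such cut-offs were combined as a panel, false positives could accumulate, by an amount that the documents do not allow one to fix.

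The result rests on reading the section 2.6 rates as any-serotype rates, on equal groups within the 350, on an even spread of serotypes and on equal background signal. Of these, the even spread and the equal background matter most. In-sample optimism arises on either reading and is larger per serotype (about 0.07) than pooled (about 0.04).

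**What to change.** In section 2.8.3:
- State the unit of the ROC, and include a child-level (any-serotype) ROC as the analysis that the sample can support.
- On either reading, report bootstrap intervals for the cut-offs and optimism-corrected sensitivity and specificity.
- Treat serotype-specific cut-offs as exploratory, set them from the healthy-control distribution, and give them only for serotypes with a pre-set minimum number of positives.
- Describe sensitivity as the share of clinical pneumonia cases flagged, because the cases are not confirmed as pneumococcal.

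The choice of child-level score, and of a fixed specificity or an optimal point, can stay with the sponsor; both are trade-offs.

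The cost is a few sentences and a little R code, with no new samples or tests. The price is less favourable reported performance and few serotypes with their own cut-off. With a minimum of 10 positive cases, for example, about 2-10 of 24 would qualify in an even mix and about 3 in a 1/rank mix.
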